## Consent Plan Complete

Protocol Progress:

- **INITIAL SETUP**
- **BACKGROUND, RATIONALE & GOALS**
- **RESEARCH PLAN**
- **CONSENT PLAN**
- ⑤ **RISKS, PRIVACY & CONFIDENTIALITY**
- ⑥ **POPULATIONS WITH SPECIAL CONSIDERATIONS**
- ⑦ **INSTITUTIONAL REQUIREMENTS**
- ⑧ **DOCUMENTS**

Click Continue below to go to the next section

## Risks, Discomforts, Potential Harms and Monitoring

- 1. \* Describe the risks of each research procedure to participants or others. For each identified risk, provide an assessment of the anticipated seriousness and likelihood of the risk. Some examples of possible risks include but are not limited to:**
  - **Physical risks (e.g. bodily harms or discomforts, side effects, etc.)**
  - **Psychological risks (e.g. emotional, mental, or spiritual harms or discomforts, changes to thoughts, beliefs, or behaviors, etc.)**
  - **Research data risks (e.g. loss of confidentiality and privacy)**
  - **Social or legal risks (e.g. impacts on relationships or reputation, legal or criminal justice actions for self or others, etc.)**
  - **Financial risks (e.g. impacts on income, employability, or insurability, loss of services, etc.)**
  - **Other risks (e.g. unforeseeable risks of experimental procedures, risks related to particular study designs (randomization, washout, placebo, withholding care/services, deception), etc.)**

See the help text for additional guidance.

The potential physical or psychological risks to participants are minimal and do not exceed those that would be incurred by students who do not participate. The potential participants in this study currently receive community-based education and training as planned in this proposal. The only additional risks to participants would be loss of confidentiality or possible exposure to negative comments about their disabilities from employees or customers of the employment training sites.

In addition, students and parents may find some of the questions we ask during discomforting or distressing. If that is the case, students or their parents may skip that question, ask us to stop that line of questioning, or ask us to stop the interview at any time.

- 2. \* Describe how each of the risks/harms/discomforts identified above will be minimized:**

Study records will be maintained in locked storage areas with access only to individuals engaged in the research. No information about the study will include information that can be used to directly or indirectly identify participants. This statement refers to both reporting and storage of study data. One person on the research team will have a unique identifier code list all protocols and electronic data will be coded with that unique identifier. The list will be encrypted on a password protected computer and will be maintained in paper copy in a locked filing cabinet. Thus, stored electronic and paper data will be separated from the unique identifier code. No individual will be referenced in any reporting of data.

Support personnel will be available to provide education and counseling to participants. In the event that a participant required professional services from a psychologist or behavioral counselor, support personnel will refer that individual to properly licensed services. Participants will access these services at their own cost through their own resources including insurance or other funding.

We can guarantee that all locations where the Project SEARCH research intervention occurs will be EEOC compliant, however, we cannot guarantee that, once a participant leaves the intervention, their future job will be at an EEOC compliant location.

During the COVID-19 crisis, we will not be holding any face-to-face or in person interactions. We will hold all meetings via phone or video conference. We will have at least two research staff on the phone or video conference. We will also email all forms to participants. Finally, we will have research staff ensure that they are in a private space in their homes away from others overhearing the conversation. We will ask participants to do the same if they wish.

- 3. \* Describe any potential risks or harms to a community or a specific population based on study findings (e.g. information that could be stigmatizing or derogatory):**

There are no potential risks or harms to a community or specific population based on the study findings known.

- 4. Where appropriate, discuss provisions for ensuring necessary medical, professional, or psychological intervention in the event of adverse events to the subjects:**

There are no plans to provide medical, professional, or psychological intervention to participants in the study. If such services are needed by participants, we will refer them to their own medical doctors or another community doctor, psychologist or psychiatrists. Participants will bear financial responsibility for that care. The types of events that may result in referral to a student's home doctor includes minor first aid emergencies, illness, or visible signs of emotional distress, such that the student cannot continue with their daily activities. There is no person individually responsible for making such determinations. Rather the site coordinator on-site will be trained in first aid and will address any minor emergencies as they occur. We will notify ORSP and HRPO of any reportable events immediately upon becoming aware of the event. We will comply with all audits and reviews of our research procedures and protocols. Additionally, We will notify ORSP and HRPO of any additional risks discovered in the conduct of this research.

**5. \* Describe criteria for when the investigator would withdraw an individual participant from the study; such as safety or toxicity concerns, emotional distress, inability to comply with the protocol, etc.:**

As noted previously, participants who are placed in the community based employment training program will not go to their home high school. Instead, they will receive their education in the employment training program. In the event that a participant can no longer participate in the study due to emotional distress or inability to comply with the study protocol, we will contact the participant or their LAR, and the placing home school division to ensure a smooth transition from the study back to their home high school.

**6. \* Summarize any pre-specified criteria that would trigger the investigator/sponsor/monitoring committee to stop or change the study protocol due to safety concerns:**

In the event that the study site becomes unsafe, or the findings indicate significant risk to participants, we will stop the study. In doing so, we will contact the participant or their LAR, and the placing home school division to ensure a smooth transition from the study back to their home high school. We will review all potential sites to ensure their compliance with safety procedures prior to initiating any off site employment training. This review will include ensuring that the community employment training site in question meets all VCU emergency procedures including fire, OSHA, and inclement weather safety protocols.

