**3. Eligibility screening prior to consent and how those activities will be carried out (when applicable)**

**See the help text for additional guidance.**

Students will be recruited through their schools through (a) a flyer advertising an informational meeting for students and parents with information about the study; (b) a letter to students and parents sent by the school, and (c) regularly scheduled Individualized Education Plan (IEP) meetings at which parents and students attend. Information about the study will be provided to students and to their families.

Potential participants will submit an application that contains their contact information. (See Application for Participation located in the recruitment materials sections).

Recruitment activities will be held from January through May of years 1 and 2. Recruitment may occur in year 3 if there is significant attrition of participants. Once all participants are enrolled and identified, we will assign a number to each enrolled participant and complete randomization using a random numbers generator on a computer. The individual completing randomization will not know the identity or group to which individuals are assigned.

Recruitment procedures will be completed as follows:

1. Each school district representative who participates on the coordinating team will schedule an informational meeting in their school division for potential participants from their schools.
2. Applications and flyers announcing informational meetings will be sent to all school district representatives to share with potential participants in January of years 1, 2, and potentially 3.
3. Informational meetings will be held at the times and in the locations identified by the school district representatives.
4. If potential participants or their family members are unable to attend the informational meetings, VCU staff will meet with them at a time and location of their choosing.
5. At each informational meeting, potential participants and their family members will receive an application with instructions on how to apply, when and where to deliver completed applications.
6. VCU staff will answer any questions from potential participants regarding the research.
7. Upon receipt of the application, VCU staff will coordinate with the screening team to schedule screening interviews in a private location that is convenient to the potential participant and their family members.

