**See the help text for additional guidance**

This is a randomized, wait-list controlled study of the efficacy of the Project Search plus ASD Supports Model (PS+ASD) in 32 adolescents and young adults aged 18 to 22 with ASD. Approximately 32 subjects will be enrolled and randomized in a 1:1 ratio to treatment or wait-list control. A sufficient number of potential subjects will be screened to achieve this number of enrolled subjects.

The six dependent variables in question are the primary endpoint employment rate (upon completion and at 12 months and 18 months post-enrollment) and the secondary endpoints hourly wages, hours/week, Social Responsiveness Scale total score, Behavior Assessment System for Children 3rd Ed. Anxiety and Depression t-score and the Quality of Life Questionnaire percentile score at baseline (Baseline), 12 months post enrollment (12 months), and 18 months post-enrollment (18 months). The efficacy of the intervention will be analyzed by comparing the differences in these six variables between the treatment group and the control group.

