## Data Retention

**1. \* Select all of the ways that individually identifiable information obtained during pre-screening and/or screening will be handled for individuals who DO NOT qualify for the study:**

- N/A - study does not require screening procedures
- Immediately destroy the information and identifiers (no data collected)**
- Immediately destroy the identifiers connected with the data (anonymization)
- Store until the end of study & then destroy
- Use as "screening failure" data by members of the study team
- Provide to others outside of the research team (with the participant's permission)
- Request permission from participant to maintain and use the identifiable information
- Other

**2. \* Will participants be able to withdraw their data (paper, electronic, or specimens) from the study (e.g. ask that it be destroyed or returned) if they no longer wish to participate? (FDA-regulated studies should select No – see help text)**

- Yes
- No

**3. \* If Yes , describe the process (oral, written, email, letter, etc.) that participants should use to request withdrawal of their data/specimens. Identify if there is a timepoint when withdrawal will no longer be an option and/or if the amount of data that can be withdrawn is reduced at different points in the study.**

Participants will contact study staff and request to withdraw from the study. Study staff will contact the participants school division personnel and inform them of the participant's decision to withdraw. Study staff will work with school division staff to ensure a smooth transition back to the home school division.

**4. \* What will happen to the research materials (e.g. data, specimens, documents, etc.) when the research has been completed?**

- Stored indefinitely with identifiers removed
- Stored indefinitely with identifiers attached
- Destroyed at the end of study once the minimum time required for data retention has been met per VCU Data Retention Policy and/or sponsor retention requirements**
- Destroyed when notified by sponsor but not less than the minimum time required for data retention per VCU Data Retention Policy
- Other

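### Leaving the programme is written as leaving the study, with no follow-up or all-randomised analysis to offset it, so the employment effect may be inflated

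*Combined protocol and SAP*

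**What the plan says.** Under Risks, Discomforts, Potential Harms and Monitoring, item 5 asks when the investigator would withdraw someone from the study. The answer first notes that "participants who are placed in the community based employment training program will not go to their home high school". It then takes the case of a participant who "can no longer participate in the study due to emotional distress or inability to comply with the study protocol", and says that the team will contact the participant or representative and the school division "to ensure a smooth transition from the study back to their home high school".

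Data Retention, item 3, asks how participants can withdraw their data. The answer describes the same route: "Participants will contact study staff and request to withdraw from the study", after which "Study staff will work with school division staff to ensure a smooth transition back to the home school division".

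Study Procedures, item 4, on recruitment, says: "Recruitment may occur in year 3 if there is significant attrition of participants". It does not say whether those recruits add to or replace earlier participants.

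The design description (Study Procedures, item 6) makes employment rate the primary endpoint, at completion and at 12 and 18 months after enrolment, and compares the treatment group with the control group. The sample-size justification (Study Population, item 3) names Fisher's exact test at a two-sided 5% level. Neither section defines an analysis set, a rule for unknown employment status or an allowance for dropout.

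**The concern.** Stopping an intervention and leaving a trial are different events, and here one sentence covers both. Going back to the home school presupposes having left it, which item 5 says only of those placed in the programme. The exit therefore belongs, in practice, to the treated arm. The reasons given, distress and inability to comply, could plausibly go with a lower chance of later employment.

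If staff follow the text as written and stop contacting these students, loss on the primary endpoint depends on the arm and perhaps on the outcome. The comparison would then be programme completers against all controls. With 16 treated participants, each person missing from the denominator moves the rate by several points. Because the analysis set is not named, the choice between a completer and an all-randomised comparison also stays open until outcomes are known.

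**Working it through.** **Inputs from the documents.** 16 treated and 22 controls; pilot employment 87% versus 6.7%; programme employment 60% to 90% across sites; Fisher's exact test, two-sided 5% (all Study Population, item 3). About 32 participants at 1:1 (Study Procedures, item 6), which does not match 16 and 22, so both sizes were run. Community employment of 4.1% to 11.8% (Background, item 1).

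**Assumptions.** The number withdrawn, w = 1 to 4 of 16, or a 25% or 50% chance that each non-employed treated participant is lost. The documents give neither figure.

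**Step 1: the plan's own figure.** Summing both binomial distributions over every table with Fisher p ≤ 0.05, for 87% versus 6.7% with 16 and 22, gives power above 0.999. This agrees with the stated power of more than 0.80.

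**Step 2: inflation if failures leave the denominator.** With k truly employed of 16 and w non-employed dropped, the observed rate is k/(16 − w) and the inflation is k/(16 − w) − k/16.

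| Truly employed | Dropped | Observed rate | Inflation (points) |
|---|---|---|---|
| 10/16 = 62.5% | 1 | 10/15 = 66.7% | 4.2 |
| 10/16 | 2 | 10/14 = 71.4% | 8.9 |
| 10/16 | 3 | 10/13 = 76.9% | 14.4 |
| 10/16 | 4 | 10/12 = 83.3% | 20.8 |
| 14/16 = 87.5% | 1 | 14/15 = 93.3% | 5.8 |
| 14/16 | 2 | 14/14 = 100% | 12.5 |

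Ten of 16 lies near the bottom of the quoted programme range and 14 of 16 near the pilot rate. At 14 of 16 only two failures exist, so 12.5 points is the ceiling.

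**Step 3: does significance at the planned contrast depend on this?** Suppose 87% is the rate among those who stay and the w who leave count as not employed. The all-randomised rate is 0.87 × (16 − w)/16, that is 81.6%, 76.1%, 70.7% and 65.25% for w = 1 to 4. Exact Fisher power against 6.7% with 22 controls is 0.9996, 0.9979, 0.9925 and 0.9794. The test result is safe; the estimate differs by 0.87 × w/16, or 5.4, 10.9, 16.3 and 21.75 points.

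**Step 4: no true effect.** Both arms share one employment rate, and each treated non-employed participant is lost with probability 0, 25% or 50%. Exact enumeration, 16 versus 16:

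| Common rate | Bias (points), 25% / 50% lost | False significance favouring treatment, 0 / 25% / 50% lost |
|---|---|---|
| 6.7% | 2 / 6 | 0.1% / 0.8% / 2.9% |
| 11.8% | 3 / 9 | 0.5% / 2.1% / 5.7% |
| 30% | 6.4 / 16.2 | 0.9% / 3.6% / 9.6% |
| 50% | 7.1 / 16.7 | 1.0% / 3.2% / 8.7% |

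At 6.7% with 16 versus 22, the last column becomes 0.4%, 1.8% and 3.9%. At that rate the total two-sided error stays below 5% with either set of sizes. The 30% and 50% rows are well above the control rates the documents report.

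**The case against.** Item 5 answers an ethics-form question about safety withdrawals. It describes a handover to the school and is not an analysis rule. A reader might infer four things that the documents do not support.

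- *Withdrawn participants are removed from the analysis.* No section says so. The analysis set is unstated.
- *Those who leave are mainly unsuccessful.* This is plausible, but no number, arm split or employment outcome is given for anyone who leaves.
- *The bias must favour the programme.* Any participant may withdraw under Data Retention, and Background names relocation and deployment, which could remove people from either arm.
- *Year-3 recruits fill the places of those lost.* The recruitment text does not say that they replace anyone.

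The published text is also not the whole file. The grant narrative and the human-subjects procedures are listed as attachments but not reproduced, and consent pages are not shown; follow-up after withdrawal could be described there. Under Data Retention, withdrawing oneself or one's data is a participant's right, and no remedy should override it. The larger null-case figures need employment rates that the documents do not support for controls.

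All of this stands, and it makes the point conditional. It does not remove it. Item 5 is more than silence: it states that the participant goes from the study back to school, and nothing visible says that outcome collection continues.

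**Conclusion.** The point holds as a conditional one. Leaving the programme for distress or inability to comply is written as leaving the study; in practice the route applies to the treated arm; and the published text provides neither follow-up nor an all-randomised analysis for those who take it. If these participants are lost and mostly not employed, the employment effect may be inflated. The plausible size is about 4 to 21 points at a true 10 of 16 with one to four lost, and at most 12.5 points at 14 of 16. Under no effect at the documented 6.7% control rate, losing 25% to 50% of treated failures adds about 2 to 6 points. What is at risk is the size of the effect, not significance at the planned contrast. The figures rest on assumed withdrawal numbers, on every person dropped being not employed, and on no loss among controls. The change should be made because it is cheap and protects the primary endpoint.

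**What to change.** - **Withdrawal criteria (item 5).** State that return to the home school ends programme participation only. Employment status is still collected at completion, 12 and 18 months unless the participant or representative withdraws consent for follow-up. When a participant leaves the programme is not changed.
- **Data Retention, item 3.** Separate three requests: leaving the programme, declining further follow-up and withdrawing data already collected.
- **Primary comparison.** Analyse all randomised participants in their assigned arm.
- **Unknown employment.** Count it as not employed in both arms. This rule could itself favour the programme if more controls are lost, so add a sensitivity analysis that counts unknown treated participants as not employed and unknown controls as employed. Report losses by arm and reason.
- **Year-3 recruitment.** State that these are additional randomised participants and that everyone randomised earlier stays in the analysis.

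The cost is protocol wording and a few extra interviews using the existing 12- and 18-month script. The observed treated rate may be somewhat lower; with up to four of 16 counted as not employed, power at the planning rates stays at about 0.98.

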**Data and Safety Monitoring**

**Data and safety monitoring is a system for checking the study's data at regular intervals over the study period to identify and address issues that could affect the safety of research participants. This requirement is in accordance with 45 CFR 46.111.**

**The purpose of data and safety monitoring plan is to set forth study team procedures for monitoring/addressing:**

- Participant safety (physical, psychological, etc.)
- Data validity
- Early stopping (termination) based upon changes in risks and benefits.

**7. \* Indicate if this study will have a Data Safety Monitoring Board (DSMB) or a Data Safety Monitoring Plan (DSMP): [Required for all greater than minimal risk studies]**

DSMB

DSMP

No DSMB/DSMP [Note: This response is not applicable for greater than minimal risk studies]

# Privacy

Privacy refers to an individual's right to control how others view, record, or obtain information about them. When privacy is violated it can involve such things as

- Being asked personal questions in a public setting;
- Being publicly identified as having a particular characteristic or diagnosis;
- Being seen entering a place that might be stigmatizing;
- Being photographed, videotaped or observed without consent;
- Disclosure of personal information to unauthorized people

Privacy is not the same as confidentiality because privacy protections apply to people, and confidentiality protections apply to data. Confidentiality protections should be described on the Data Confidentiality page of this form, not here.

Instructions for this page:

Select all the applicable ways that the research team will protect participants' privacy throughout the course of the study. The options listed include some of the most common best practices. Not all will be applicable to every study.

\*\*The IRB will expect studies to operationalize all selected checkboxes into the conduct of the research.

To elaborate on any response, also click the "Other Protections" checkbox to provide further explanation in the last free-text question.

Read the entire page before filling out the form.

1. \* Protections when conducting one-on-one in-person interventions or interactions (for groups see Q2 below):

- Conducting study activities in locations that maximize privacy (limited people around, closing doors, drawing drapes around beds, monitoring voice volume, etc.)
- Verifying identity before discussing personal information.
- Asking the participant if they are comfortable answering questions in that location
- Asking the participant if they are comfortable with having other people present (if any)
- Moving away from other people when conducting activities in public spaces or offering a private space
- Offering other options of ways to respond to sensitive questions (i.e. pointing, clicking, or writing) if uncomfortable verbally responding
- Using generic signs on research rooms and spaces, particularly for research on stigmatizing or sensitive topics
- Other protections not listed in this question – describe below
- N/A – study has no in-person interventions or interactions with participants

2. \* Protections when conducting group interventions or interactions:

- Conducting study activities in locations that maximize privacy (limited people passing by, closing doors, monitoring voice volume, etc.)
- Moving to a more private area to answer questions or to discuss concerns
- Discussing privacy with the participants and the importance of not talking outside the group about what other people say during the group session
- Allowing participants to use a pseudonym or limiting use of individuals' names during the group activity
- Asking everyone in a public group setting (e.g. classrooms, workshops) to turn something in (blank or filled) so participants do not have to self-identify when turning in materials
- Collecting paper forms in a closed box or envelope rather than passing to others or leaving in an open area
- Limiting participant identifiers that would be visible on paper documents (i.e. using study IDs instead of direct identifiers)
- Allowing people to distance themselves from other participants during group activities
- Offering other options of ways to respond to sensitive questions (i.e. pointing, clicking, or writing instead of speaking)
- Using generic signs on research rooms and spaces, particularly for research on stigmatizing or sensitive topics

- Ensuring non-participating individuals are not captured on recordings or in photos
- Other protections not listed in this question – describe below
- N/A – study has no group interventions or interactions

**3. \* Protections when conducting remote interventions or interactions (e.g. phone, text, email, video-conference, tele-health, online, etc.):**

- Conducting study activities in locations where study staff can maximize their own privacy (limited people around, closing doors, monitoring voice volume, etc.)**
- Leaving/sending generic messages that avoid using study and participant identifiers, such as names, study titles, clinics, study topics, etc.**
- Obtaining permission prior to sending text messages**
- Advising the participant to move to a location where they are comfortable answering questions and will not be overheard - incorporate this instruction into your study materials**
- Advising online participants to complete the activity at a time and location where they will be comfortable answering questions - incorporate this instruction into your study materials
- Ensuring non-participating individuals are not captured on recordings or in photos
- Offering other options of ways to complete the activity (i.e. online, paper, phone) if more privacy is desired**
- Offering a way to save and return later to the online activity if privacy is compromised
- Other protections not listed in this question – describe below
- N/A – study has no remote interventions or interactions with participants

